6. STUDY PROCEDURES

Interventions: For up to seven days, enrolled subjects will either receive 1) one-hour music listening sessions twice daily through noise-cancelling headphones, or 2) one-hour sessions consisting of a silence track twice daily through noise-cancelling headphones.

a. Music Intervention: Twice daily one-hour intervention will be delivered based on our extensive playlist created by our board-certified music therapist consultant and used in our previous studies. The playlist contains relaxing slow tempo instrumental music (60-80 beats/minute). Featured instruments in the playlist include piano, harp, reed, guitar and Native American flute. The mix features classical music and relaxing melodies and does not contain lyrics or spoken words. In addition to the twice daily music intervention sessions, patients will be encouraged to self-initiate listening to slow-tempo music from the study playlist whenever desired as a means to engage in quiet time or listening enjoyment. Our iPad® app will efficiently log all of the 'as desired' music listening sessions by automatically capturing frequency, length, and music selections for both the twice daily music intervention sessions as well as the self-directed listening sessions. Variability in self-directed music listening duration and frequency will be used as a covariate in subsequent analyses.

b. Attention Control: A silence only track will be added to the study iPads® and will be activated in the form of an app similar to the music listening tracking app. Patients randomized to this arm will receive a noise cancellation headphone-applied condition identical to the music intervention experimental treatment; twice daily one hour-sessions. Likewise, patients will have the opportunity to use the silence app with headphones whenever desired. As with the music intervention, the app will track each session's length, frequency, and self-directed headphone application with the silence track.

[figure not shown]

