- **Delirium/Coma Free Days:** Delirium/coma free days will be the primary outcome for the trial. Delirium/coma free days are the number of days after randomization patients are alive free of delirium and not in coma during the seven-day study intervention phase. This outcome describes the duration of normal cognitive status where the patient is not comatose and does not have delirium and has been utilized in high impact studies. 14-17 We will utilize the Confusion Assessment Method for the ICU (CAM-ICU)75 and the Richmond Agitation Sedation Scale (RASS)⁷⁶ for assessment of delirium and coma respectively. RASS score ranges from -5 to +4 with a score of -4 or -5 (lack of response to verbal or physical stimuli) characterized as comatose and ineligible for CAM-ICU assessments. RASS scores of -3 and -2 depict moderate and light sedation, -1 drowsiness, 0 alert and calm, and +1 to +4 various degrees of agitation. Patients with a RASS score of -3 to +4 will be considered eligible for CAM-ICU assessments. The CAM-ICU score will be determined by examining the patient for (a) acute or fluctuating changes in mental status, (b) inattention, (c) altered level of consciousness and (d) disorganized thinking. Patients will be considered delirious if they display (a), (b), plus (c) and/or (d). Trained research assistants will be performing CAM-ICU twice daily after the assigned intervention. Sedation status through RASS will be collected before and after the intervention delivery. After the 7-day study intervention phase, study staff will continue to assess RASS and CAM-ICU twice daily throughout the subject's hospital stay (up till day 28).
- **2. Delirium Severity**: Delirium severity will be assessed twice daily by trained research assistants using the CAM-ICU-7 developed by [name]. CAM-ICU-7 is a seven-point scale (0-7), derived from the RASS and the CAM-ICU. The CAM-ICU-7 score ranges from 0-7; categorized as 0-2: no delirium, 3-5: mild to moderate delirium, and 6-7: severe delirium. Trained research assistants will be performing CAM-ICU-7 twice daily after the assigned intervention. After the 7-day study intervention phase, study staff will continue to assess CAM-ICU-7 twice daily throughout the subject's hospital stay (up till day 28).

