3. STATISTICAL CONSIDERATIONS

Statistical Analyses: We will compare baseline patients' demographic characteristics (age, gender, race and levels of education) between the intervention and control group using two sample t-tests for continuous variables and Chi-square tests for categorical variables to determine whether the two groups are balanced in these variables. Variables that are found to be unbalanced will be included as covariates in all models comparing outcomes between the two groups. Intention to treat approach will be used in all analyses.

a. Primary Specific Aim: Delirium/coma free days by day 7 will be compared using analysis of covariance (ANCOVA) model with group (intervention versus control) as the independent variable while adjusting for the baseline patients' demographic variables not balanced between the two groups. For patients discharged before day 7, the days from discharge to day 7 will be counted as delirium/coma free. For patients who died before day 7, 0 delirium/coma free days will be counted from date of death to day 7. We have used the same approach in our previous trials and this approach is able to appropriately handle potential missing data due to discharge or death of patients before day 7.¹⁷

Secondary Specific Aim 1: Mixed effects models will be used to compare delirium severity (CAM-ICU-7), pain (CPOT) and anxiety scores (VAS-A) measured twice daily from randomization to day 7, time of death or discharge. In each of the models, repeated CAM-ICU-7, CPOT or VAS-A scores will be the outcome variable respectively. Group, time, group and time interactions will be included as independent variables while adjusting for potential baseline covariates. Significant group and time interactions will indicate differences in changes of these outcomes between the two groups. Post-hoc analyses will be conducted to determine the earliest times when significant differences between these outcomes can be detected. We will compare various variance covariance structures including autoregressive (AR) and variance components blocked by time of the day (am versus pm) using the likelihood ratio tests to determine the most appropriate covariance structure. We will also examine potential non-linear trajectories of change in these outcomes by including quadratic time in the models and by fitting spline models.

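### Self-directed music listening, which arises after randomisation, is promised as a covariate with no model named; in an ANCOVA of the two arms it would change what the group coefficient estimates

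*Combined protocol and SAP*

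**What the plan says.** Section 6 (Study Procedures), item a, gives music patients two one-hour sessions a day and adds that "patients will be encouraged to self-initiate listening to slow-tempo music from the study playlist whenever desired". The app logs this use, and the paragraph ends: "Variability in self-directed music listening duration and frequency will be used as a covariate in subsequent analyses". Item b gives control patients the same freedom with the silence app and logs "self-directed headphone application with the silence track", but the covariate sentence names music listening only.

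The primary outcome, in the same section, counts days on which the patient is "alive free of delirium and not in coma during the seven-day study intervention phase". Coma is defined by RASS, with "a score of -4 or -5 (lack of response to verbal or physical stimuli) characterized as comatose".

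Statistical Considerations sets out the models:

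- **All analyses:** "Intention to treat approach will be used in all analyses".
- **Primary aim:** ANCOVA on group, adjusted for baseline "demographic variables not balanced between the two groups". Item d adds sex to every analysis.
- **Secondary aim 1:** mixed models. "Group, time, group and time interactions will be included as independent variables while adjusting for potential baseline covariates".
- **Secondary aim 2:** ANCOVA on group with baseline covariates. Item c adds variables associated with loss to follow-up, drawn from a comparison of baseline characteristics.
- **Exploratory aims 1 and 2** (May 2023 amendment): a mixed model and ANCOVAs respectively, with stratification variables and baseline covariates.

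Self-directed listening appears in none of these lists.

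**The concern.** The covariate sentence is a firm commitment, not limited to an exploratory or within-arm analysis. The variable it names differs from every other covariate in the plan. It is generated after randomisation, is one component of the treatment being tested, and accumulates over the same seven days in which the primary outcome is counted. A patient at RASS -4 or -5 presumably cannot start a session, so the outcome itself may determine the covariate. That is an inference; the documents give neither the sign nor the size of any association.

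If listening enters a between-group model, the comparison is no longer protected by randomisation. If it does not, there is no bias, but the protocol then contains an unfulfilled commitment. As written, the choice of model and coding could be made after the data are seen, and the working below shows that the answer can depend heavily on it.

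**Working it through.** **1. The plan's own figures.** For 0.5 SD, two-sided alpha 0.05 and 80% power, the exact two-sample t-test needs 63.77, so 64 per arm or 128 in total (power 80.1%). 128 / (1 - 0.20) = 160. Both stated numbers reproduce. With 80 per arm the power is 88.2%. The sample size is not at issue; 0.5 SD serves as the yardstick.

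**2. What adjustment does in the ANCOVA.** Set listening L to zero in control and include no other covariates. The control arm then carries no information on the slope, and least squares gives exactly:

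adjusted group coefficient = (difference in means) - b x (mean of L in the music arm),

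where b is the slope of outcome on L within the music arm. This held to rounding error in every simulated trial. The coefficient is the contrast at L = 0.

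With r the listening-outcome correlation in the music arm and CV = SD/mean of L, b x mean = (r / SD) x mean in outcome SDs, so the shift is -r/CV. Neither quantity is in the documents. Assumed range, in SD:

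| r | CV 0.75 | CV 1 | CV 1.5 |
|---|---|---|---|
| 0.2 | -0.27 | -0.20 | -0.13 |
| 0.3 | -0.40 | -0.30 | -0.20 |

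A negative r reverses the sign and inflates the estimate.

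**3. Simulation for the primary outcome.** 20,000 trials per setting, 80 per arm, outcome SD 1. Listening has no causal effect and is L = max(0, 0.3 + c y + sqrt(1 - c^2) e), with e standard normal. About 62% of music patients then listen at all. Under the null, mean L is 0.567, SD 0.683 and CV 0.683 / 0.567 = 1.205. The latent link c = 0.2 / 0.3 / 0.5 corresponds to r of about 0.18 / 0.27 / 0.45, and -r/CV gives -0.150 / -0.225 / -0.375, matching the simulation.

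| Analysis | True effect 0 | True effect 0.5 SD |
|---|---|---|
| No listening covariate | 0.00 | 0.50, power about 88% |
| Control coded zero | -0.15 / -0.23 / -0.37; false positives 13 / 24 / 57% | 0.34 / 0.25 / 0.05; power 44 / 26 / 6% |
| App use in both arms, equal behaviour | 0.00 | 0.48 / 0.46 / 0.39 |
| Centred within the music arm | 0.00; false positives 5-6% | 0.50 |

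With c = -0.2 and control coded zero, the null becomes +0.15 and 0.5 becomes 0.64.

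**4. Infrequent listening.** If only 20% of music patients self-initiate (CV about 2.7), 4,000 trials per setting gave null estimates of -0.05 / -0.07 / -0.13 with false positives of 7 / 7 / 12%. A true 0.5 SD was estimated at 0.45 / 0.41 / 0.33, with power 77 / 71 / 54%. With 10% listening, the null estimates were -0.03 / -0.04 / -0.07.

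**5. Listening as a working part of the treatment.** A separate simulation used 64 per arm, mean use about 1.03 units and a true effect of assignment of 0.50 SD. If each unit adds 0.25 SD, with no confounding, the adjusted coefficient is 0.25 (0.50 - 0.25 x 1.03 = 0.24). If each unit adds 0.5 SD, it is -0.01. The adjustment removes the part of the benefit that passes through listening. With no link at all the coefficient stays at 0.50, but its standard error rises from 0.18 to 0.26 and power falls from 79% to 46%.

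**6. Mixed models.** 1,500 trials per setting, seven daily values, exchangeable correlation 0.4, average listening stable over days under the null, listening entered as a main effect with control coded zero, c = -0.2 or -0.3. The group-by-time estimate stayed at 0.00 under the null and between -0.096 and -0.101 for a true -0.1 SD/day. The group main effect moved by +0.10 to +0.65 SD.

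**The case against.** The best defence is that the sentence was never meant for the group comparison. It sits in the intervention description, directly after the text on app logging, and speaks of variability in listening, which fits an exposure-response analysis among music patients. The statistical section specifies the primary model and invokes intention to treat, so it can reasonably be read as governing. This reading is plausible, and under it there is no bias. But no text says so, and intention to treat is commonly understood as fixing who is analysed and in which group; it does not by itself exclude a covariate.

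A second point is that control patients' self-directed use is logged too, so the covariate could exist in both arms. That coding is much milder: no bias under the null if behaviour is equal, and attenuation of 0.5 SD to 0.48 / 0.46 / 0.39. The sentence names only music listening, however, and app use in both arms is still measured after randomisation and may itself respond to assignment.

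Third, the larger distortions need frequent listening and a strong link. This stands: many patients enrolled on a ventilator may never self-initiate, and step 4 shows the bias is then modest at the weaker links. It does not vanish. Finally, the quantified harm concerns the primary ANCOVA only. No link was computed for the three-month or biomarker outcomes, and no bias is claimed for the group-by-time tests.

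**Conclusion.** The concern holds and should be fixed. The gap in the text is certain: section 6 commits to a post-randomisation covariate that every specified model omits, and nothing reconciles the two. The harm is conditional on the sentence being applied to a group comparison. For an ANCOVA with control coded zero and no other covariates, the change in meaning is exact algebra; its size is -r/CV in outcome SDs.

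Under the assumed positive links it ranges from a few hundredths of an SD when few patients listen to 0.37 SD under the null (0.45 SD when the true effect is 0.5 SD) when about 62% do and the link is strongest. A negative link would favour music. Listening rates, links and coding are assumptions, since the documents supply none.

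**What to change.** Replace the covariate sentence in section 6, item a, and repeat the replacement in Statistical Considerations:

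> Self-directed music listening and silence-app use will be summarised by arm and will not be covariates in the between-group intention-to-treat models of the primary, secondary and exploratory aims; any analysis using listening (for example, exposure-response within the music arm) will be exploratory.

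This agrees with the models already specified and keeps the logged data available for an exposure analysis. Covering every aim is a matter of consistency with the intention-to-treat statement, not a claim that each has been shown to be biased. The cost is a wording change, with no effect on data collection, sample size or clinical care. It should be made before outcome data are examined by arm.

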- **b. Secondary Specific Aim 2:** ANCOVA models will be used to compare IU-TBANS, PHQ-9, and GAD-7 collected at three months post hospital discharge with group as the independent variable while adjusting for potential baseline covariates.
- **c. Missing Data:** We expect up to 20% of patients who may not complete the primary outcome at day 7 due to death in the ICU or discharge before day 7. We will conduct sensitivity analyses with varying assumptions for the patients with missing outcomes to determine the robustness of our findings. The mixed effects model we propose for Secondary Aim 1 is robust to the missing at random assumption and is unbiased if we include all relevant covariates in the model. We will also compare baseline characteristics of patients with 3-month

assessment and those who are lost to follow-up and adjust for the variables associated with missing data to ensure unbiased estimation and inference.

d. Sex as a Biological Variable: Both male and female patients will be included in the trial. We do not anticipate treatment efficacy will differ by sex. We will include sex as a covariate in each analysis to

determine whether estimated treatment effects differ by sex.

e.Sample Size and Power: Sample size estimation is based on the observed effect size from our pilot data where the intervention group had higher delirium/coma free days from the control group with estimated effect size of 0.52. Using two sample t-test, we estimate that we will need 128 total patients with complete data to detect an effect size of 0.5SD or higher at α =0.05. For robustness of results, we also estimated power if we assume Poisson distribution for mean delirium/coma free days with a total 128 patients observed at day 7, we will have 98.7% power to detect group difference at α =0.05 using the nonparametric Wilcoxon test. Allowing up to 20% attrition rate for patients dropping out before day 7, we will enroll 160 total patients for this trial (80 per group).

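### The plan does not say how comatose assessments enter the delirium-severity model; if music reduces coma, the model can mask a benefit and in some scenarios give a wrong-direction estimate

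*Combined protocol and SAP*

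**What the plan says.** Section 6 (Study Procedures), under Delirium/Coma Free Days, describes RASS -4 or -5 as "characterized as comatose and ineligible for CAM-ICU assessments". It adds: "Patients with a RASS score of -3 to +4 will be considered eligible for CAM-ICU assessments". Under Delirium Severity it says: "CAM-ICU-7 is a seven-point scale (0-7), derived from the RASS and the CAM-ICU". No CAM-ICU-7 value, imputation or exclusion rule for coma is given. Under Anxiety, the VAS-A is scored from a mark that the patient makes.

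Section 3 (Statistical Considerations), Secondary Specific Aim 1, fits mixed models to CAM-ICU-7, CPOT and VAS-A scores "measured twice daily from randomization to day 7, time of death or discharge". On the model terms: "Group, time, group and time interactions will be included as independent variables while adjusting for potential baseline covariates". On the test: "Significant group and time interactions will indicate differences in changes of these outcomes between the two groups". Item c, Missing Data, calls this model "robust to the missing at random assumption and is unbiased if we include all relevant covariates in the model". The missing-data text deals with death, discharge and loss to follow-up. It does not mention coma. Its sensitivity analyses name no assumptions and follow directly on a sentence about the day-7 primary outcome.

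**The concern.** Whether a severity score exists depends on the patient's level of consciousness, which lies on the same continuum as the outcome. The trial also hopes to change that state: coma counts against a patient in the primary outcome, and lower sedative exposure is part of the rationale in section 2.

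A patient who leaves coma for delirium has improved by the trial's own logic, yet starts to contribute high CAM-ICU-7 scores. A patient who stays comatose contributes none. If music wakes patients, the two arms' severity averages come from differently selected assessments. A real benefit could then be understated, or the estimate could have the wrong sign. Readers could not tell a change in severity from a change in who could be assessed.

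**Working it through.** **The plan's own figures.** The plan gives no coma rate and no figure for coma-related missingness, so there is nothing to reproduce on the point itself. The one figure given for the CAM-ICU-7 model is 80.6% power. With 64 patients per arm, 0.2 SD per day, AR(1) correlation 0.4 (stated for the VAS-A only) and days 1-7, a linear slope test has 99.9% power, so that figure was not reproduced. Nothing below rests on it.

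**Step 1: does the stated condition hold?** Unbiasedness is claimed if all relevant covariates are included. The covariates named are baseline ones. Coma is a post-randomization state that treatment may alter, so baseline values cannot account for it. The mixed model also borrows from a patient's other scores. That helps when there are scores before or after coma, but a patient comatose throughout contributes no record.

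**Step 2: composition example (all inputs assumed).** Control assessments: 25% coma, 50% delirious (mean 5.5), 25% clear (mean 1). Music moves 10 percentage points out of coma; a fraction p of these become delirious and the rest clear. Score 7 for coma is used only as a contrast.

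- Control, observed: (0.50×5.5 + 0.25×1)/0.75 = 4.00. With coma = 7: 0.25×7 + 3.00 = 4.75.
- p = 100%, observed: (0.60×5.5 + 0.25×1)/0.85 = 4.18, difference +0.18 (music worse). With coma = 7: 0.15×7 + 3.55 = 4.60, difference -0.15.
- p = 50%, observed: (0.55×5.5 + 0.30×1)/0.85 = 3.91, difference -0.09. With coma = 7: 0.15×7 + 3.325 = 4.375, difference -0.375. The direction is right, but most of the contrast is hidden.
- Break-even: the woken assessments average 5.5p + 1(1-p) = 1 + 4.5p. Setting this to 4.00 gives p = 0.67.

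With p = 100% and shifts of 5 to 15 points, the observed difference runs from +0.09 to +0.25, against -0.08 to -0.23 with coma = 7.

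**Step 3: the planned type of test.** Step 2 compares means at one time point, whereas the plan tests group by time. Trials were therefore simulated with 64 patients per arm and 14 half-day assessments in three states: coma, delirium and normal. Assumed: 20-60% comatose at the start, 30-70% of awake patients delirious at the start, mean severity about 5 if delirious and 1 if not. An AR(1) group-by-time model was fitted to non-comatose scores, then again with coma = 7. There were 60 to 70 trials per scenario. Positive means music worse.

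| Waking effect | Slope/day, observed | Slope/day, coma = 7 | Day-7 difference, observed | Day-7 difference, coma = 7 |
|---|---|---|---|---|
| From the start, rate ×3 (5 scenarios) | -0.072 to +0.012 | -0.164 to -0.041 | +0.07 to +0.23 | -0.97 to -0.37 |
| From three or four days in, rate ×6 to ×8 (4 scenarios) | +0.040 to +0.076 | -0.150 to -0.075 | +0.39 to +0.61 | -0.92 to -0.49 |

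A further early-waking run, with faster recovery from delirium, gave a slope of -0.044 and a day-7 difference of -0.01, against -0.125 and -0.91 with coma = 7. The late scenarios also used a lower control waking rate (0.02 per assessment, against 0.04) and a larger multiplier, so they differ from the early ones in more than timing. The Monte Carlo standard error of the late slopes was 0.010 to 0.012.

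Across the nine tabulated scenarios, a significantly worse slope for music appeared in 0-6% of trials, and a significantly worse fitted day-7 difference in 5-26%.

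**The case against.** Severity among patients who can be assessed is a legitimate secondary quantity, and the primary outcome already counts coma as a bad state. Scoring coma as 7 puts it in the band the protocol calls severe delirium, which changes the construct; the negative figures above depend on that choice. This stands, and it is why the planned model should stay and any score for coma should be called a convention. It does not settle the matter, because assessable patients are a subgroup selected after randomization.

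Four stronger readings are tempting, but the documents do not support them:

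- *That the protocol says CAM-ICU-7 is not scored in coma.* It says so only for the CAM-ICU. For the CAM-ICU-7 it is a reasonable inference. If the sponsor intends to score coma, the rule is still missing.
- *That the plan calls the model unbiased without qualification.* The claim is conditional. The criticism is that the condition is unlikely to be met.
- *That severity will point the opposite way to the primary endpoint.* With p = 100%, clear assessments are 25% in both arms, so the primary is unchanged. Opposite signs in the example need p between about 67% and 100%, and the observed difference is then below 0.18. Simulated delirium/coma-free days favoured music on average in the nine tabulated scenarios (+0.03 to +0.33), but a run with no treatment effect gave +0.07, so the smallest of these are indistinguishable from zero.
- *That the VAS-A is biased in a known direction.* No direction or size was worked out for it. The protocol also reports very little missing VAS-A data in earlier studies, although section 2 places the earlier music trial in the latter part of ventilation, so that experience may not carry over.

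**Conclusion.** The concern holds as a statement of what can happen. The plan leaves comatose assessments unaddressed in the CAM-ICU-7 model, and probably in the VAS-A model, and its unbiasedness condition is unlikely to be met with baseline covariates.

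The main risk is masking. With early waking, the fitted slope mostly still favoured music, but by less than in the coma = 7 contrast. A wrong-direction estimate is possible in some scenarios: in the example, when more than about 67% of woken assessments are delirious; in the simulations, clearly for the slope when a strong waking effect came late. A significantly worse interaction was rare.

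All sizes rest on assumed coma rates, delirium shares and severity means. The point affects secondary outcomes only; the primary outcome does not share the gap.

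**What to change.** - Keep the planned CAM-ICU-7 mixed model, and label its result as severity among assessable (non-comatose) assessments.
- Prespecify a companion CAM-ICU-7 analysis that places RASS -4 or -5 assessments in a top ordered category, or at score 7 as a stated convention and not a true severity value.
- Report by arm the share of CAM-ICU-7 and VAS-A assessments missing because of coma.
- Under Missing Data, restate the unbiasedness claim as an assumption that coma-related missingness may violate.

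The cost is one extra model and one table. RASS is already recorded four times daily in the intervention phase, so no new data are needed. The drawback is that the value given to coma is a convention, which is why this is a companion analysis and not a replacement. It should be fixed before unblinding, so that it cannot look like a rescue of a disappointing result.
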